Although the ICTs care for patients over the age of 18,¹⁰ most of the patients referred to ICTs are older – in January 2017, 61% were aged 75 or over and only approximately 5% were aged under 50.¹¹ They tend to have long-term conditions, complex care needs or are approaching the end of their life.

The ICT models were launched in all localities on 27 July 2015, at which time their core teams were in place and they were ready to see referred patients. The ICT models were not prescriptive and developed organically in each locality (Farnborough, Farnham, Yateley, Fleet and Aldershot), to best meet the local needs. For example, anecdotally, two of the ICTs, in Farnborough and Aldershot, are getting more referrals for patients with mental health issues, while another, Farnham, may be seeing more patients with dementia.

By April 2017, a total of 885 patients had been referred to ICTs across the five localities.¹² By June 2017, 1,051 patients had been referred. Although all the ICTs were launched in July 2015, they have developed at different paces, with varying levels of referrals (Figure 1). In January 2017, 25 new patients were referred in Farnborough, 19 in Farnham, 19 in Yateley, 12 in Fleet and 9 in Aldershot.⁶ This is equivalent to between 0.04% and 0.1% of the local population, depending on the locality.⁶ Over time, the Vanguard is aiming to expand to the top 2% of patients in need.

Figure 1. Number of patients referred to ICTs each month in each of the five localities

Source: NEHF CCG

Up to June 2017, patients were predominantly referred to the ICTs based on a clinical judgement, rather than through the application of pre-defined eligibility criteria. The majority of referrals came from GPs, though referrals were also received from other health care workers (eg community staff, mental health, social care).¹⁰ For example, it has been reported that in January 2017, 84 patients were referred to ICTs across the 5 localities, of which 53 were referred by GPs (63%), 14 by community staff, 11 by social care staff, 1 by mental health staff and 1 from the Medically Fit for Discharge list from Frimley Park Hospital.

Only four of the patients referred in January 2017 were reportedly identified from the predictive modelling tool Johns Hopkins ACG [Adjusted Clinical Groups] system.^{6,13}

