Matching will be done without replacement if possible (i.e. each intervention patient will be matched to a unique patient in the control group). If, however, it is difficult to find balanced groups, matching will be done with replacement, that is, the same control patient can be matched to several intervention patients. Additionally, as a same potential control patient will be assigned monthly index dates, the same control patient may also be matched to several intervention patients, but with different index dates (and correspondingly potentially slightly

different baseline characteristics). The IAU will match 1:1, that is, one control patient to each intervention patient.

The genetic matching algorithm will try various distance functions to determine the 'closeness' of the match. However, for some variables a match may be required to be exact or to fall within a pre-fixed 'caliper', whereby the variables are required to be within a fixed distance of one another. Table 4 shows those variables where special matching methods are to be applied.

Table 4. Matching variables and method of matching

Variable	Method of matching
Living at home, in a nursing home or in a residential care home	Exact

The IAU will match within each locality separately to ensure that the intervention patients have access to the same PACS services as their control patients and ensure balance within each locality.

It is expected that all intervention patients will be matched to controls.

As the IAU is not matching on length of time in the study (as this could be correlated with quality of care), the intervention and their control patients may differ in this respect. The IAU will conduct descriptive analyses regarding length of time in the study, and address differences using an offset in the model which will allow for differences in time at risk.

Choice of matching variables

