Type of endpoint	Outcome	Initial model	Alternative model	Diagnostics
Count data	Number of admissions / A&E attendances/outpatient visits	Poisson	Negative binomial / Zero-inflated Poisson	Over-dispersion Model fit Excess zeros
Proportions	Proportion of emergency/elective bed days (of whole follow-up period)/ Proportion of deaths in hospital/ Proportion of patients who die (sensitivity analysis)	Binomial	Quasi-binomial/Negative binomial	Model fit Distribution of model residuals Over-dispersion Heteroscedasticity diagnostics

To account for differing attrition arising from death, moving away from the area or different entry dates into the study, an offset of the number of days in the study will be added to the model. However, the offset assumes that the number of days that are ‘missing’ is random and that the rate of outcomes, for instance emergency admissions, is constant, when in fact this is unlikely to be the case. For example, a patient may use more hospital services in the final months of life. The IAU will examine the length of time people were followed up in the study and reasons for leaving the study between the groups. As detailed in the section on Index dates and follow-up period (p. 23), a patient’s follow-up period ended (was censored) when the patient either died, moved away from NEHF or the study period ended. If the length of time patients were followed up in the study or the reasons for leaving the study differed between the groups, the IAU will consider doing an alternative analysis as a sensitivity analysis.

Subgroup analysis

As the localities have differed in how they implemented the ICTs and which patients they targeted, as well as in what other interventions they offered outside of the ICTs (see Table 1), the IAU will aim to do a subgroup analysis by locality. However, there is a risk that the data are so sparse in some localities that models cannot be fitted in those localities. If the models can be fitted, the results are unlikely to show statistically significant results due to small sample sizes; however, a comparison between localities may nonetheless provide learnings to NEHF as to whether the effect is homogenous across sites and if not, which locality may be showing most potential.

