It is well known that mental and physical health are interrelated and that when the mental health needs of people with physical health conditions are not adequately addressed, this also negatively impacts on physical health outcomes.^{43,44} People with mental ill health have several times higher rates of A&E attendances, emergency admissions and ACS emergency admissions than those without.⁴⁴ NEHF has included mental health professionals in the

ICTs, providing appropriate care for patients with mental health problems. As a subgroup analysis, sample size permitting, the IAU will identify patients with a history of mental ill health and evaluate the effect of ICTs on the defined outcomes (independent of whether the attendance or admission was primarily for a physical or mental need) on this subgroup. The mental health subset cohort will be classified as those who can be identified in hospital data as having had a diagnosis for mental ill health, that is, those who had at least one inpatient admission or outpatient appointment with a diagnosis of any mental and behavioural disorder (ICD-10, Chapter V, codes F00 to F99),⁴⁵ or, where the main specialty (medical specialty under which the hospital consultant is contracted) was mental health (NHS specialty codes 700 to 715)⁴⁶ within the previous three years. The subset will include those with a serious mental illness, such as schizophrenia, bipolar disorder or psychosis, as well as less severe mental ill health. The definition is similar to that of previous research,⁴⁴ but identifies patients with any diagnosis, whether primary or secondary, while the previous research only included those with a primary diagnosis of mental ill health.

Sensitivity analyses

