The results of all tested regression models will be presented in the technical appendix to the report, to show if the effect size and significance of the selected best model were sensitive to the choice of model.

Sample size calculation

No sample size was calculated for this study. The analysis is considered informative and will be carried out regardless of whether our study population is of a sufficient size to detect a statistically significant difference.

3. Limitations and sources of bias

Threats to validity

Internal validity

One of the main threats to the validity of this study is unobserved confounding. Unobserved confounding can occur at area, hospital, general practice or patient level. There is always a risk of unobserved confounding in non-randomised studies, but here the risk is larger due to the way patients have been selected for the ICTs, especially up to June 2017 when patients were primarily selected based on clinical judgement. This leads to potential selection bias. The majority of referrals come from GPs, though referrals are also received from other health care workers (e.g. community staff, mental health, social care).¹⁰ The lack of information on any non-clinical reasons for referring patients (for example, a close family member dying or moving away), together with a lack of primary care and community data, makes it difficult for us to identify what characteristics the referred patients were selected on and therefore to identify a matched control group that is similar to the intervention group in these characteristics. The uncertainty of the results due to potential unobserved confounding will not be reflected in the confidence intervals or p values, as these capture other kinds of uncertainties. Therefore, even a statistically significant result will need to be interpreted with caution. The IAU will perform some sensitivity analysis (see section on Sensitivity analysis, p. 31) to try to assess the presence of unobserved confounding.

If important predictive covariates are omitted from the matching and regression models, then unobserved differences between the groups may contribute to any or part of any difference in outcomes. These differences would in turn then erroneously be attributed to the intervention.

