There may also be positive unintended consequences of the ICTs on the comparator group, for example if communication and relationships across organisational boundaries improves as a result of staff participation in the ICTs.

Statistical conclusion validity

The IAU is expecting a sample size of approximately 900 patients. This may be too small a sample size to identify a significant effect at conventional 95% significance levels if the effect is small or there is large variability within the groups.

A recent evidence review suggested that initiatives aiming to better manage patients 'at risk' are often highly valued by patients but seldom reduce hospital activity.¹⁸ There are several contributing factors, including limitations of risk stratification tools to identify patients before they deteriorate and that these initiatives often identify unmet need and provide more timely access to care.¹⁸ A limitation of our study is that the IAU cannot distinguish between additional hospital activity that is due to good and timely care and other hospital activity. However, by evaluating the number of ACS hospital admissions, we may be able to identify any reductions in emergency admissions due to good quality primary and community care.

Construct validity

The success of an ICT is in both correctly identifying patients who would benefit from additional help and in the care they receive. This evaluation takes into account the effect of the ICTs on the patients referred to them and not the effect of the patient selection process (i.e. identifying patients most at risk who may benefit from the ICT).

SUS data is an administrative database and has not been subjected to the cleaning rules that the Hospital Episode Statistics database is. However, the IAU Data Management team will perform data checks and cleaning.

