Modelling options also included adjusting for only a list of 'core' variables and those variables considered most predictive of the outcome, as the low number of events for some of the outcomes may otherwise have led to over-parametrised models. The most predictive variables were identified by running a lasso regression and where possible included all core variables as a minimum.⁵⁷ Variables considered 'core' were: age; gender (male or not male); IMD quintile; locality; Charlson Index; number of Elixhauser comorbidities; number of frailty comorbidities; history of mental ill health; index date quarter; hospital use in year prior to index date; and emergency admissions, CACS emergency admissions and UCS emergency admissions in the two months prior to index date.

Due to low numbers of care home residents (<10) in both ICT and matched control groups, analyses only adjusted for whether patients lived at home or in a care home (i.e. no differentiation between nursing and residential homes).

Following the analysis, it was found that outpatient appointments included community data from Virgin Care Services that had been uploaded to SUS in error. These appointments were removed from the data and the analysis of outpatient hospital use was redone. Other outcomes were not reanalysed; therefore in the case where these analyses adjusted for outpatient appointments in the year prior to the study, this variable would have contained some community outpatient appointments from Virgin Care Services.

Modelling options did not include multilevel models with locality as a random effect, as five localities were considered too few groups to adequately run such a multilevel model.

Acknowledgements

We are grateful to the North East Hampshire and Farnham CCG team for their support and their review and feedback on an earlier version of this statistical analysis protocol. We are also grateful to [name] and [name] for their peer review comments on an earlier version.

References

- ¹ NEHF CCG. Happy, Healthy, at Home (accessed 29 June 2017). Available from: www.northeasthampshireandfarnhamccg.nhs.uk/about-the-ccg/happy-healthy-at-home
- ² Moran P. Short Stay Emergency Admissions. NEHF CCG, available on request. 2016.

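### The plan judges effect homogeneity and the most promising locality from separate, underpowered locality models, with no treatment-by-locality interaction or heterogeneity test

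*Protocol*

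**What the plan says.** The Summary says that, if the sample is large enough, each of the five localities will be looked at separately. The Subgroup analysis section in Methods repeats the aim, warns that models may not be fittable in some localities, and concedes that significance is unlikely. It still proposes that "a comparison between localities may nonetheless provide learnings to NEHF as to whether the effect is homogenous across sites and if not, which locality" shows most potential.

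Locality appears in three other places that matter here:

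- Baseline variables: matching is done within locality, and locality goes into the regression models as a covariate.
- Statistical analysis: a multilevel model with locality as a random effect is listed as an option, to capture differences in outcomes between localities and to sharpen local estimates. No random treatment effect is mentioned.
- Addendum, Statistical analysis: "Modelling options did not include multilevel models with locality as a random effect", on the ground that five groups are too few. No replacement is named.

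The required outputs in the Reporting section include no heterogeneity test, and the forest plot there is by outcome measure, not by locality. On size, "The IAU is expecting a sample size of approximately 900 patients" and "No sample size was calculated for this study".

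**The concern.** Whether an effect is the same across sites is a question about differences between effects. Five separate estimates, each with its own interval, do not answer it. One of the five always comes first, and localities with few patients give the most extreme estimates.

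The plan expects non-significant locality results, so in practice the reading would rest on how far apart the point estimates lie. It gives no rule for deciding when that distance is more than chance. The results are meant to give the commissioner learning about its localities, so an apparent front-runner could attract attention for no reason other than noise.

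**Working it through.** The plan states no power or subgroup error rate, so there is no figure of its own to reproduce.

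**Inputs from the protocol**
- About 900 ICT patients (Statistical conclusion validity).
- "The IAU will match 1:1, that is, one control patient to each intervention patient" (Identifying control group), with matching done within locality.
- Locality sizes, from Integrated care teams: "In January 2017, 25 new patients were referred in Farnborough, 19 in Farnham, 19 in Yateley, 12 in Fleet and 9 in Aldershot". These sum to 84, which agrees with the stated total.
- The 95% level (Statistical conclusion validity); two-sided 0.05 is assumed.

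**Inputs that are assumptions**
- Events per patient and negative binomial dispersion k, which the protocol does not give.
- Mean follow-up of 0.75 to 1 year, within the stated 1 to 23 months.
- The split of the 900 between localities.

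**Formula.** For a count outcome with n pairs, mean μ events per patient and dispersion k, SE(log RR) = √[(2/n)(1/μ + k)].

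**Step 1: roughly equal localities (900/5 = 180, or 150 allowing for losses), identical true effects**
- n = 180, μ = 1.0, k = 1.0: √[(2/180)(2.0)] = 0.149.
- n = 150, μ = 0.8, k = 1.5: √[(2/150)(2.75)] = 0.191.
- The expected range of five independent standard normals is 2.326. The expected highest-to-lowest ratio is therefore exp(2.326 × 0.149) = 1.41 to exp(2.326 × 0.191) = 1.56.
- By simulation (200,000 draws), the ratio exceeds 1.4 in 50% and 73% of studies respectively.

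**Step 2: the January 2017 split applied to 900**
- 900 × 25/84 = 268, 900 × 19/84 = 204 (twice), 900 × 12/84 = 129, 900 × 9/84 = 96.
- With 1 event per patient-year, 1 year and k = 1, the SEs are 0.122, 0.140, 0.140, 0.176 and 0.204.
- The rate ratio detectable with 80% power is exp(−2.80 × SE): 0.71, 0.68, 0.68, 0.61 and 0.56 by locality. For all 900 it is 0.83.

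**Step 3: the same split, true RR 1.0 in every locality**
- The median RR in the best-looking locality is 0.84. The chance that it is 0.90 or lower is 76%.
- The median worst-to-best ratio is 1.43.
- The smallest locality ranks first in about 26% of studies, the largest in about 16%.
- Over 18 scenarios (0.5, 1 or 2 events per patient-year; k = 0, 1 or 2; 0.75 or 1 year), the median best RR is 0.77 to 0.92. The chance of a best RR at or below 0.90 is 37% to 86%. It is under 50% only in the two scenarios with 2 events per patient-year and no over-dispersion.

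**Step 4: reading by significance instead**
- At least one of five localities nominally significant: 1 − 0.95⁵ = 22.6%. In the benefit direction: 1 − 0.975⁵ = 11.9%.
- Best against worst locality at p < 0.05: about 26% when all effects are equal. A joint 4-df test holds 5%.
- If RR is 0.8 everywhere, some but not all localities show a significant benefit in 73% to 94% of studies (four rate and dispersion combinations, 1 year). That pattern could be misread as heterogeneity.

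**Step 5: power of the joint test.** With RR 0.8 in one locality and 1.0 in the other four, power is 9% to 37%, depending on which locality differs and on five rate and dispersion combinations at 1 year.

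**The case against.** The best case for the plan is that it is candid and cautious. It states the low power, says only that a comparison may be informative, and looks for a leading locality only if the effect is not the same everywhere. It asks for confidence intervals and p values, and treats the results as pointers for further investigation. The main study question is the overall effect of ICT referral, and separate models do serve the stated aim of estimating impact in each setting. Separate fitting in the Subgroup analysis section is implied rather than spelt out, though the Summary does say the localities will be looked at separately.

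Much of this stands. Low power is not concealed, and locality estimates are worth reporting. What remains is that the plan makes its search for a leading locality depend on a judgement of homogeneity, and supplies no method for that judgement.

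A reader might infer three stronger points that the protocol does not support:

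- That losing the random effect removed a safeguard against noisy locality effects. As described, it concerned outcomes, so it was not clearly a way to shrink treatment effects.
- That the mental ill health analysis has the same fault. There, "As a subgroup analysis, sample size permitting, the IAU will identify patients with a history of mental ill health" and estimate the effect within that group. A contrast with other patients is needed only if a differential benefit is claimed.
- That chance would usually produce a significant locality. The figure is about 23% per outcome. Chance differences are common in the ranking and spread of point estimates, not in nominal significance.

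**Conclusion.** The point holds in this form: the plan proposes to judge homogeneity, and to identify the locality with most potential, from separate underpowered models without any interaction or heterogeneity test. With identical true effects, a highest-to-lowest rate ratio spread of about 1.4 to 1.6 is to be expected from chance.

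That size rests on assumed event rates, dispersion and roughly equal localities. It applies to the count outcomes, not to average length of stay. With high event rates and no over-dispersion the spread is smaller (median ratio about 1.2). The January 2017 split is one month's referrals and may not represent the whole period; if it does, the smallest locality is the likeliest to rank first by chance.

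This should be changed, but it affects the locality comparison only. It does not undermine the overall effect estimate.

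**What to change.** For each outcome, fit one pooled model with a treatment-by-locality interaction. Report the joint 4-df test together with all five locality estimates and their 95% confidence intervals, on a forest plot labelled exploratory. State that no locality will be named as most promising on point estimates alone, and that a non-significant test does not show homogeneity because its power is low.

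The locality estimates should be shown whatever the test result. Falling back to the pooled effect alone when the test is non-significant would treat low power as evidence of a common effect.

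The cost is one extra model term and one test per outcome, with no new data. The Addendum describes work already done, so a test added now should be labelled as a later addition.

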There may also be positive unintended consequences of the ICTs on the comparator group, for example if communication and relationships across organisational boundaries improves as a result of staff participation in the ICTs.

Statistical conclusion validity

The IAU is expecting a sample size of approximately 900 patients. This may be too small a sample size to identify a significant effect at conventional 95% significance levels if the effect is small or there is large variability within the groups.

A recent evidence review suggested that initiatives aiming to better manage patients 'at risk' are often highly valued by patients but seldom reduce hospital activity.¹⁸ There are several contributing factors, including limitations of risk stratification tools to identify patients before they deteriorate and that these initiatives often identify unmet need and provide more timely access to care.¹⁸ A limitation of our study is that the IAU cannot distinguish between additional hospital activity that is due to good and timely care and other hospital activity. However, by evaluating the number of ACS hospital admissions, we may be able to identify any reductions in emergency admissions due to good quality primary and community care.

Construct validity

The success of an ICT is in both correctly identifying patients who would benefit from additional help and in the care they receive. This evaluation takes into account the effect of the ICTs on the patients referred to them and not the effect of the patient selection process (i.e. identifying patients most at risk who may benefit from the ICT).

SUS data is an administrative database and has not been subjected to the cleaning rules that the Hospital Episode Statistics database is. However, the IAU Data Management team will perform data checks and cleaning.

As the IAU only has access to the monthly table extracts from NHAIS and there is no date of when between the monthly snapshots a change occurred, index and end dates are sometimes approximated, using the date of the data extraction. As a result, the number of days in the study, which will be used to determine the offset in the models, will also only be approximate in some cases. Also, patients who move may only register with a new general practice once they need to be seen by a GP. Therefore the patient registration data may contain a time lag. However, as the population in this study consists of patients with complex needs and multi-morbidity, this time lag is not expected to be large, nor do we expect it to be unbalanced between the groups.

There are some limitations in the outcomes that the IAU will be analysing. The benefit of a home visit rather than having to travel to an outpatient appointment will not be reflected in the data or our outcomes. Similarly, the benefit of a prompt assessment on quality of life or longer-term health will not be apparent in our outcomes.

Other limitations

The IAU will not be able to evaluate other potential impacts of the Vanguard programme, such as quality of life or improvement in working relationships, as the IAU only had access to secondary care data. Costing secondary care data is not within the scope of this study.

This study cannot explore how the ICTs or other interventions have changed over time, for instance changes to the core members of an ICT team, and the effect this may have had on the outcomes.

The IAU evaluation will be supplemented by the local evaluation, conducted by Wessex Academic Health Science Network.

4. Reporting

General reporting considerations

Results will be reported as the relevant measure of effect, such as odds or rate ratios, plus 95% confidence intervals and p values. Absolute numbers may also be presented, where appropriate. Both the post-matching unadjusted and adjusted analysis will be presented and the variables used in the adjustment noted. Results will be presented to 2 decimal places for effect size and confidence intervals. P values will be shown to 2 significant digits.

Special reporting requirements for this study

At a minimum, the following are requirements for this study:

- adherence to the STrengthening the Reporting of OBservational studies in Epidemiology (STROBE)⁵³ and the REporting of studies Conducted using Observational Routinely-collected Data (RECORD) guidelines⁵⁴
- adherence to the NHS Digital (previously Health and Social Care Information Centre, HSCIC) small number rules⁵⁵
- compliance with the statistical code of practice.

Tables and figures for reporting matching results

Tables

A baseline table showing descriptive statistics for the intervention group and the matched and unmatched control populations, with:

- 1.0 continuous variables summarised by mean (standard deviation, SD) or median (interquartile range, IQR) depending on the distribution
- 2.0 categorical variables summarised by number (%)
- 3.0 standardised differences calculated for the intervention group versus the unmatched and matched control groups, and variance ratio for continuous variables.

Figures

The following figures would be a minimal requirement:

- 1.0 dot plot showing the standardised differences from both the matched and unmatched sample
- 2.0 bar chart of comorbidities from both the matched samples.

Histograms illustrating the baseline characteristics of the intervention and matched control groups in more detail will be produced and reviewed by the IAU team. If histograms are to be included in the report, then these will be rebanded if necessary to ensure minimum cell counts of above 10.

Tables and figures for reporting statistical results

Tables

The following tables will be presented as a minimum:

- 1.0 A table showing the unadjusted estimates of treatment effect for the intervention and matched control groups:
 - 1.1 for binary outcomes the number and proportion in each group
 - 1.2 for count data the number of events and person time of exposure
 - 1.3 for continuous data the mean and standard error
 - 1.4 the size of the measure effect (e.g. odds ratio, rate ratio, hazard ratio or mean difference) together with a 95% confidence interval.

- 2.0 A table showing the adjusted results:
 - 2.1 the size of the adjusted measure together with a 95% confidence interval and p value
 - 2.2 all adjustment variables should be listed.

Figures

The following figures would be a minimal requirement:

- 1.0 forest plot showing the adjusted results for each outcome measure.

Tables and figures for sensitivity analyses

The following tables may be produced for the appendix:

- 1.0 a table for showing study length and reasons for censoring (leaving the study).

Data cleaning and validation checks

Data cleaning and data validation checks will be performed by the IAU Data Management team, in accordance with the IAU Data Management Quality Assurance Process. Where appropriate, a summary of the results can be produced for the technical appendix.

Data flow diagrams

The following diagrams will be produced for the technical appendix:

- 1.0 data linkage process diagram
- 2.0 data flow diagram of study cohort selection.

5. Addendum

This section has been added to the original statistical analysis protocol (SAP) document to provide further clarifications and information on modifications to the original SAP. The original SAP was agreed in September 2017 with this section added in July 2018.

Definition of study cohort, page 18

In addition to the exclusion criteria described on page 18 of this document, the following exclusion criteria were applied prior to the analysis:

- Patients with no valid Lower Layer Super Output Area (LSOA) geographic area – this variable was used to determine a patient’s level of socioeconomic deprivation
- For potential control patients, patients more than 2 years’ older than the oldest ICT patient or more than 2 years’ younger than the youngest ICT patient – this was to limit the size of the dataset of potential controls in the matching process

Study endpoints, page 21

Here we provide further clarification on how variables were defined.

Elective admissions are defined as those that are ‘ordinary’ or day cases and exclude maternity and regular day/night cases.

When calculating readmission rates, the NHS Outcomes Framework guidance⁵⁶ was followed, with the exception of also including elective day cases as potential offsets for the calculations. This was consistent with the definition of elective admissions described above, which includes both ‘ordinary’ and day cases.

For the variable average length of stay in the year prior to the index date, any hospital spell that starts in the pre-period but continues into the follow-up period was included in its entirety within the pre-period. For the outcome measure average length of stay in the follow-up period, we only included spells that both start and finish within the follow-up period. There is no expected bias between the ICT and matched control groups, as both had access to the same hospitals.

The IAU identified a number of ‘overlapping’ in-patient spells (stays) in the SUS data where, for example, a patient spell with one provider did not end before a spell with another provider started. When calculating average length of stay, we did not account for these overlapping spells. Instead, the average length of stay was calculated for each spell, as recorded in the data. Note: For the outcomes emergency bed days and elective bed days, bed days were not double-counted, that is the number of unique days in hospital following either emergency or elective admission were calculated.

Duplicate outpatient appointments were removed. Outpatient appointments relating to mental health services, to the extent these were recorded in the outpatient data, were included.

Index dates and follow-up, page 24

To further limit the size of the dataset of potential controls, only one potential index date per quarter was created for potential patients aged less than 65 years. Only 14% of ICT patients in the study were younger than 65 years.

Baseline variables, page 26

The variables mental ill health and serious mental ill health, as defined on page 32, were included as baseline variables, replacing the mental health definition specified in IPOPAEGP.

Connective tissue disease in the IPOPAEGP was not included as a baseline characteristic, as it overlapped with the Elixhauser definition of rheumatic arthritis. The Elixhauser variable peripheral vascular disorders was not included in error.

Identifying control group, page 28

Due to low numbers of care home residents that were referred to ICTs (<10), matching on type of residence (ie whether a person lived at home, in a nursing or a residential care home) was not done by exact matching.

Matching parameters, page 29

Due to the size of the dataset of potential control patients (approximately 750,000 records), the parameters for the genetic matching algorithm was limited to iterations based on population size 200, maximum generation 100 and number of generations to wait 10.

Statistical analysis, page 30

Modelling options also included adjusting for only a list of 'core' variables and those variables considered most predictive of the outcome, as the low number of events for some of the outcomes may otherwise have led to over-parametrised models. The most predictive variables were identified by running a lasso regression and where possible included all core variables as a minimum.⁵⁷ Variables considered 'core' were: age; gender (male or not male); IMD quintile; locality; Charlson Index; number of Elixhauser comorbidities; number of frailty comorbidities; history of mental ill health; index date quarter; hospital use in year prior to index date; and emergency admissions, CACS emergency admissions and UCS emergency admissions in the two months prior to index date.

Due to low numbers of care home residents (<10) in both ICT and matched control groups, analyses only adjusted for whether patients lived at home or in a care home (i.e. no differentiation between nursing and residential homes).

Following the analysis, it was found that outpatient appointments included community data from Virgin Care Services that had been uploaded to SUS in error. These appointments were removed from the data and the analysis of outpatient hospital use was redone. Other outcomes were not reanalysed; therefore in the case where these analyses adjusted for outpatient appointments in the year prior to the study, this variable would have contained some community outpatient appointments from Virgin Care Services.

Modelling options did not include multilevel models with locality as a random effect, as five localities were considered too few groups to adequately run such a multilevel model.

Acknowledgements

We are grateful to the North East Hampshire and Farnham CCG team for their support and their review and feedback on an earlier version of this statistical analysis protocol. We are also grateful to [name] and [name] for their peer review comments on an earlier version.

References

- ¹ NEHF CCG. Happy, Healthy, at Home (accessed 29 June 2017). Available from: www.northeasthampshireandfarnhamccg.nhs.uk/about-the-ccg/happy-healthy-at-home
- ² Moran P. Short Stay Emergency Admissions. NEHF CCG, available on request. 2016.
